2.2.3 Pharmacokinetic experience and dose justification

The PK/PD profile of BIVV009 in healthy volunteers and in patients has been established based on the data collected from the first-in-human clinical trial. A human PK model was constructed from the complete and final Phase 1a data. This model was then augmented with the available PK data emerging from the Phase 1b component of this trial, and the combined model was used to simulate a variety of possible dose regimens for use in patients. The dose regimen proposed for use in current and future clinical trials with BIVV009, including Study BIVV009-03, differs from that used in the Phase 1a and 1b program because weekly IV administration was deemed to be logistically challenging for patients when the period of treatment is increased from weeks to

months. A regimen based upon a single priming dose on Day 0, followed by bi-weekly dosing on Days 7, 21, 35, 49, etc. can provide continuous, complete C1s inhibition while better accommodating to the needs of patients. Human PK modeling suggests that a dose level of 6.5 grams or 7.5 grams (based on body weight of <75 kg or ≥75 kg, respectively) is necessary to protect patients better from potential restoration of CP activity at the end of the inter-dose interval. The weight cut-off of 75 kg was chosen based on the expected weight distribution in CAgD patients with a median weight of 74.8 kg.

The in vitro and in vivo pharmacologic profile of BIVV009 has two especially important features that help to define the optimal dose regimen for clinical use. First, BIVV009 has very high affinity and selectivity for C1s, with negligible off-target activity. Second, it is a potent CP inhibitor with such a steep concentration-effect relationship that it behaves as a switch-like inhibitor of C1s: at concentrations of BIVV009 ≥20 µg/mL, CP activity is virtually undetectable; at BIVV009 concentrations below this threshold the CP is fully active. This property results in the requirement to maintain a blood concentration of BIVV009 that is always at least ≥20 µg/mL, even at trough, lest CP activity be fully restored.

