4.4 DURATION OF THE STUDY

The planned total study duration per patient is approximately 2.5 to 3.5 years:

- Screening/Observation Period: 6 weeks (Day -42 through Day -1)
- Part A treatment period: 25 weeks (Day 0 through Day 175)
- Part A EOT visit: 1 week after administration of the last dose of study drug during Part A (Week 26/Day 182)

Patients who complete study Part A per protocol through the EOT visit will participate in Part B, the long-term safety and durability of response extension phase of the study.

- Part B safety and durability of response extension phase: bi-weekly dosing starting at Week 27 visit. For individual patients, dosing in Part B may last from 2 to 3 years, depending on when the patient enters Part B. Part B will run for 2 years following completion of LPO in Part A.

- Part A/B ET/Safety Follow-up visit: 9 weeks after administration of the last dose of study drug.

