- i* BIVV009 doses of 6.5 grams (if <75 kg) or 7.5 grams (if ≥ 75 kg) based on patient's baseline body weight will be administered via IV infusion over $\sim 60 \pm 5$ minutes on Days 0, 7, and every 14 days thereafter during Part A, and every 2 weeks starting at Week 27 during Part B. Patients with underlying cardiopulmonary disease may receive a 2-hour infusion with Sponsor approval. If a patient misses a scheduled dose (outside of the 2-day window or >17 days since last dose), they must return to site (unscheduled visit) to receive another loading dose 1 week prior to the next scheduled dose. Qualifying patients at participating sites may have study drug dosed at home during certain visits in Part B, according to the rules specified in Section 10.10 Appendix J (US, the Netherlands, Norway, France, Italy, Austria, Germany, Spain, and specific amendments).
- j* During Part A, PK and PD samples will be collected at predose and 1 hour (± 15 minutes) postdose (ie, 1 hour after completion of study drug infusion) from all patients on Days 0, 7, 21, 35, 49, 63, 77, 91, 105, 119, 133, 147, 161, and 175. An additional blood sample for PK and PD analysis will be collected during the EOT visit on Day 182 or at ET if a patient withdraws early. During Part B, PK and PD samples will be collected routinely at 3-month intervals during the 1st year of treatment in Part B, and then at 6-month intervals. PK and PD samples will also be collected if a patient experiences a hematologic breakthrough event at any point during the study.
- k* AEs will be recorded from the time the patient signs the informed consent form until 9 weeks after administration of the last dose of study drug.
- l* To be performed every 3 months.
- m* Refer to the Laboratory Manual for details of sample collection during Screening.
- n* Samples will be collected for a subset of the disease-related biomarkers at Day 91 only. Refer to the Laboratory Manual for details.
- o* During Part B, a 12-lead ECG will be conducted pre- and postdose at 3 months (Day 273).
- p* During Part B, the healthcare resource utilization data will be recorded every 4 weeks.
- q* To be performed in the following order: FACIT-Fatigue first, PGIS second, PGIC third, SF-12 fourth, and EQ-5D-5L fifth.

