6.1.3 Weeks 1-25

On Days 7, 21, 35, 49, 63, 77, 91, 105, 119, 133, 147, 161, and 175, patients will undergo the following procedures before administration of the study drug:

- Serum or urine pregnancy test, if applicable, on Days 21, 49, 77, 105, 133, and 161

- Physical examination (brief)
- Vital signs
- 12-lead ECG (Day 91 only)
- Hematology panel
- Clinical chemistry panel
- Solicited symptomatic anemia assessment
- QOL assessments
 - FACIT-Fatigue: all scheduled visits
 - PGIS: Days 35, 77, and 119 only
 - PGIC: Days 35, 77, and 119 only
 - SF-12: Days 35, 77, and 119 only
 - EQ-5D-5L: Days 49, 91, and 133 only
- PK and PD sampling
- ADA: In patients who consented to the use of their blood samples for future research, PD back-up samples collected at the following time points Day 7, 35, 77, 133 and 175, may be used to assay ADA.
- Disease-related biomarkers (subset at Day 91 only); refer to Laboratory Manual for details
- Record healthcare resource utilization data since previous assessment on Days 21, 49, 77, 105, 133, and 161
- Record concomitant medications/procedures including transfusions
- Adverse event monitoring

At 0 hour, study drug will be infused via an indwelling IV catheter over a period of 60 ±5 minutes. Patients with underlying cardiopulmonary disease may receive a 2-hour infusion with Sponsor approval. Additionally, study drug infusion may be interrupted or slowed in the event of suspicion of an allergic reaction or anaphylaxis.

After completion of the infusion, patients will undergo the following procedures:

- Vital signs at 1 hour (±5 minutes) postdose
- 12-lead ECG (Day 91 only) at 1 hour (±15 minutes) postdose
- PK and PD sampling at 1 hour (±15 minutes) postdose.

Vaccinations should be administered according to [Section 6.1.1.1](#), if applicable, or [Section 10.9](#), Appendix I for Japan.

Note: Patients who miss a dose (ie, outside the dosing window or >17 days since last dose) should return to the site for an unscheduled visit 1 week prior to the next scheduled dose in order to receive an additional loading dose. The patient should then resume subsequent dosing visits every 14 days after the loading dose.

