6.1.4 End-of-treatment visit in Part A (Week 26)

On Day 182, patients will undergo the following procedures:

- Serum or urine pregnancy test (if applicable)
- Body weight
- Physical examination (full)
- Vital signs
- SLE panel
- Hematology panel
- Coagulation panel
- Clinical chemistry panel
- Urinalysis
- Solicited symptomatic anemia assessment
- QOL assessments (FACIT-Fatigue, EQ-5D-5L, SF-12, PGIS, and PGIC)
- PK and PD sampling
- ADA: In patients who consented to the use of their blood samples for future research, PD back-up samples collected at this visit, may be used to assay ADA.
- Disease-related biomarkers
- Record healthcare resource utilization data since previous assessment
- Record concomitant medications/procedures including transfusions
- Adverse event monitoring

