3.1.2. Treatment

Eligible patients will receive an IV infusion of BIVV009 over approximately 60 minutes on Day 0, Day 7, and every 14 days thereafter through Week 25 (i.e., Days 21, 35, 49, 63, 77, 91, 105, 119, 133, 147, 161, and 175). Patients who weigh less than 75 kg will receive fixed doses of 6.5 g of BIVV009. Patients who weigh 75 kg or more will receive fixed doses of 7.5 g of BIVV009. Patients who miss a dose (i.e., outside the dosing window or > 17 days since last dose) should return to the site for an unscheduled visit 1 week prior to the next scheduled dose in order to receive an additional loading dose. Patients will have an EOT visit on Day 182 (Week 26).

During the 6-month treatment period, patients will receive a transfusion if his or her Hgb level meets either of the following criteria:

- Hgb is < 9 g/dL and the patient is symptomatic, or
- Hgb is < 7 g/dL and the patient is asymptomatic.

Following completion of dosing in the 6-month treatment period, patients will continue to receive BIVV009 dosing during Part B, the long-term safety and durability of response extension phase. Part B will run for approximately one year following last patient out (LPO) under Part A.

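### The last sentence of the missed-dose note in Protocol Section 6.1.3, read plainly, puts the next dose 14 days after the extra loading dose; the sentence before it puts that dose at 7 days

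*Protocol*

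**What the plan says.** The note that closes Protocol Section 6.1.3 gives two instructions in consecutive sentences. After a missed dose, the patient "should return to the site for an unscheduled visit 1 week prior to the next scheduled dose in order to receive an additional loading dose". It then adds: "The patient should then resume subsequent dosing visits every 14 days after the loading dose".

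The 1-week rule also appears in the Synopsis (study design), in Section 4.1, in Table 3 footnote i ("to receive another loading dose 1 week prior to the next scheduled dose"), twice in Appendix J (Table 4 footnote e and the restated Table 3 footnote i), and in Section 3.1.2 of the Part A SAP ("unscheduled visit 1 week prior to the next scheduled dose in order to receive an additional loading dose"). None of these carries the 14-day sentence. They are one rule repeated, not independent confirmations.

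Three other places bear on the point:

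- **Appendix J, narrative missed-dose text.** It gives no interval, but it places the loading dose before the next scheduled visit and says that visit then takes place at the office. Table 4 footnote e likewise says the next scheduled dose is given at the site. Both indicate that the scheduled dose stands. Both concern Part B home infusion.
- **Section 2.2.3, dose rationale.** It describes a "single priming dose on Day 0, followed by bi-weekly dosing on Days 7, 21, 35, 49, etc. can provide continuous, complete C1s inhibition".
- **Table 3.** The dosing visits carry a ±2-day window, and footnote i defines the trigger: "If a patient misses a scheduled dose (outside of the 2-day window or >17 days since last dose".

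**The concern.** The two sentences fix the same visit at different times. If the loading dose comes 1 week before the next scheduled dose, that dose is 7 days away. If dosing visits then run every 14 days counted from the loading dose, it is 14 days away. Two sites could dose the same situation differently, and each could point to the protocol.

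The short interval is also what makes the extra dose a loading dose. Each patient receives the same fixed amount every time (6.5 g or 7.5 g by baseline weight), so a dose followed by a 14-day gap is simply an ordinary dose given late. A site that counts 14 days leaves out the follow-up dose just after the patient has gone 21 days without drug (14 days if Day 7 was the dose missed).

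**Working it through.** **Inputs**

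- Scheduled Part A doses (Section 4.1): Days 0, 7, 21, 35, 49, 63, 77, 91, 105, 119, 133, 147, 161, 175, which is 14 doses.
- Loading dose: L = N − 7, where N is the next scheduled dosing day (Section 6.1.3).
- Visit window: ±2 days (Table 3).
- End-of-treatment (EOT) visit (Section 4.4): "1 week after administration of the last dose of study drug during Part A (Week 26/Day 182").
- First Part B dose: Week 27, that is 27 × 7 = Day 189.

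**Step 1. The two intervals.** From the first sentence, the next dose is on N = L + 7. From the last sentence, read plainly, it is on L + 14 = N + 7.

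**Step 2. Example, Day 35 missed.** The previous dose was Day 21 and N = 49, so L = 42, which is 42 − 21 = 21 days after the previous dose.

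- 7-day reading: Days 42, 49, 63 … 175.
- 14-day reading: Days 42, 56, 70 … 168.

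**Step 3. All 12 single missed doses from Day 7 to Day 161.** The 7-day reading drops one dose and adds one, so it gives 14 doses with the last on Day 175 in every case. The 14-day reading, counted to Day 175, gives:

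| Missed day | Doses before it | L | Later doses to Day 175 | Total | Last dose |
|---|---|---|---|---|---|
| 7 | 1 | 14 | 11 | 13 | 168 |
| 21 | 2 | 28 | 10 | 13 | 168 |
| 35 | 3 | 42 | 9 | 13 | 168 |
| … | +1 each | +14 each | −1 each | 13 | 168 |
| 161 | 12 | 168 | 0 | 13 | 168 |

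A missed Day 175 dose is left out. The next scheduled dose is then Day 189, so L = Day 182 under either reading.

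**Step 4. Distance from the calendar.** Every scheduled day after Day 0 is an odd multiple of 7. So L = N − 7 is an even multiple of 7, and so is each L + 14, L + 28 and so on. Every dose after the loading dose is therefore exactly 7 days from the nearest scheduled day, outside the ±2-day window.

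**Step 5. End of Part A under the 14-day reading.** The note does not say whether the visits move, so there are two branches.

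- *Day 175 and EOT on Day 182 held fixed.* There are 13 doses, the last on Day 168, and EOT comes 182 − 168 = 14 days later instead of 7. The next dose would fall on 168 + 14 = Day 182, or wait until Day 189. Section 6.1.4 lists what happens on that first day ("On Day 182, patients will undergo the following procedures") and includes no infusion. Waiting gives 189 − 168 = 21 days, above the 17-day trigger.
- *Visits shift with dosing.* The Week 25 dose falls on Day 182, giving 13 + 1 = 14 doses, and EOT falls on 182 + 7 = Day 189. The count and the 1-week interval are kept, but both visits are 7 days later than the stated Days 175 and 182.

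**The case against.** The strongest reply is that this is loose wording and not a real conflict. *After* can mean *once it has been given*. *Resume* suggests returning to an existing pattern, and *subsequent* visits can be those that follow the next scheduled dose just named. On that reading the order is loading dose, scheduled dose at 7 days, then every 14 days.

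The literal reading also undermines itself. Footnote i treats a dose outside the 2-day window as missed, so each later dose, being 7 days off the calendar, would call for another loading dose. A site with Table 3 in hand might well see this, and the repeated 1-week rule and Appendix J point the same way.

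Most of this stands as evidence of intent: 7 days is probably what was meant. It does not make the sentence correct. The sentence names the loading dose as the point from which 14 days run, and a dosing instruction should not need other sections to rescue it.

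The practical reach is also small. The sentence appears only in the Weeks 1-25 section. Section 4.3.8 describes Part A antibody sampling in the past tense, which suggests, without proving, that Part A dosing was largely over by this amendment.

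A reader might infer more than the documents support:

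- **Each affected patient loses a dose, and EOT falls two weeks after the last dose.** This holds only if Days 175 and 182 stay fixed. Section 4.4 defines EOT both as 1 week after the last dose and as Day 182, so the other branch is open.
- **The responder result is affected.** The documents give no missed-dose rate and no link from this interval to response.
- **Complement activity would return.** Section 2.2.3 requires at least 20 µg/mL even at trough, but no figure shows that a 14-day gap after re-loading falls below it.
- **A patient's compliance band would change (SAP Section 6.5.2).** That depends on whether the loading dose and any Day 182 dose are counted.

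**Conclusion.** Wrong as written, minor, with moderate confidence. The conflict between 7 and 14 days is plain on the wording. Confidence is only moderate because a looser reading removes the conflict and is probably the intended one.

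Followed literally, the sentence drops the 7-day follow-up dose and moves all later Part A doses one week off the calendar, from 11 doses if Day 7 is missed down to none by Day 175 if Day 161 is missed. This assumes a single missed dose and visit windows still tied to Day 0; the documents do not say that windows are re-based. Whether the total is 13 or 14 doses, and whether EOT stays 1 week after the last dose, depends on whether visits move with dosing, which the note leaves open.

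**What to change.** Replace the last sentence of the note in Section 6.1.3 with: *The patient should then receive the next scheduled dose 7 days after the loading dose and continue every 14 days on the original Day 0-based schedule.*

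The other statements of the 1-week rule need no change, and the Appendix J text does not conflict with the new wording. The cost is one protocol sentence. The SAP needs no edit, because its Section 3.1.2 already states only the 1-week rule.

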6.1.4 End-of-treatment visit in Part A (Week 26)

On Day 182, patients will undergo the following procedures:

- Serum or urine pregnancy test (if applicable)
- Body weight
- Physical examination (full)
- Vital signs
- SLE panel
- Hematology panel
- Coagulation panel
- Clinical chemistry panel
- Urinalysis
- Solicited symptomatic anemia assessment
- QOL assessments (FACIT-Fatigue, EQ-5D-5L, SF-12, PGIS, and PGIC)
- PK and PD sampling
- ADA: In patients who consented to the use of their blood samples for future research, PD back-up samples collected at this visit, may be used to assay ADA.
- Disease-related biomarkers
- Record healthcare resource utilization data since previous assessment
- Record concomitant medications/procedures including transfusions
- Adverse event monitoring

6.1.5 Part B extension phase

6.1.5.1 Procedures to be performed every 2 weeks

For patients completing Part A, the following procedures will be performed every 2 weeks (beginning at Week 27) during Part B prior to administration of study drug:

- Hematology panel (until Week 79)
- Clinical chemistry panel (until Week 79)
- Solicited symptomatic anemia assessment
- Record concomitant medications/procedures including transfusions
- Adverse event monitoring

6.1.5.2 Procedure to be performed every 4 weeks

- Women of childbearing potential will undergo serum or urine pregnancy testing every 4 weeks (beginning at Week 27) during Part B prior to administration of study drug
- Hematology panel (beginning at Week 79)
- Clinical chemistry panel (beginning at Week 79)
- Record healthcare resource utilization data since previous assessment

6.1.5.3 Procedures to be performed every 3 months (unless noted otherwise)

In addition, the following procedures will be performed every 3 months beginning after Week 27 (or as otherwise noted) during Part B prior to administration of study drug:

- Body weight
- Physical examination (brief)
- Vital signs
- 12-lead ECG (once at 3 months [Day 273], and at end of treatment visit)
- Urinalysis
- QOL assessments:
 - FACIT-Fatigue
 - EQ-5D-5L
 - SF-12
 - PGIS
 - PGIC
- SLE panel (every 6 months)
- PK, PD and ADA sampling during the 1st year of treatment in Part B then every 6 months

At 0 hour, study drug will be infused via an indwelling IV catheter over a period of 60 ±5 minutes. Patients with underlying cardiopulmonary disease may receive a 2-hour infusion with Sponsor approval. Additionally, study drug infusion may be interrupted or slowed in the event of suspicion of an allergic or anaphylactic reaction.

After completion of the infusion, patients will undergo the following procedures:

- Vital signs at 1 hour (±5 minutes) postdose
- 12-lead ECG (once at 3 months [Day 273]) at 1 hour (±15 minutes) postdose, and at end of treatment visit
- PK and PD sampling (every 3 months during the 1st year of treatment in Part B then every 6 months) at 1 hour (±15 minutes) postdose.

PK, PD, and ADA samples will be collected if a patient experiences a hematologic breakthrough event (rapid fall in Hgb ≥ 2 g/dL associated with an increase in LDH/bilirubin and/or decrease in haptoglobin since the last scheduled visit).

6.1.6 Infusion of the study drug at patient's home

Home infusions will be performed at pre-selected countries/sites by a healthcare professional caregiver contingent upon completion of training delivered by the Investigator or delegated site staff member only in patients willing to be administered study drug at home, and in whom previous on-site infusions were uncomplicated (for the US, the Netherlands, Norway, France, Italy, Austria, Germany, and Spain, specific amendments) (see [Section 10.10](#), Appendix J).

6.1.7 Early termination/end of study/safety follow-up visit

Upon completion of dosing in the study, or if a patient terminates the study early, the following assessments should be completed 9 weeks after administration of the last dose of study drug:

- Serum or urine pregnancy test (if applicable)
- Body weight
- Physical examination (full)
- Vital signs
- SLE panel
- Hematology panel
- Coagulation panel
- Clinical chemistry panel
- Urinalysis
- Solicited symptomatic anemia assessment
- QOL assessments (FACIT-Fatigue, EQ-5D-5L, SF-12, PGIS, and PGIC)
- ADAs against BIVV009
- PK and PD sampling
- Record healthcare resource utilization data since previous assessment
- Record concomitant medications/procedures including transfusions
- Adverse event monitoring

If a patient experiences a hematological breakthrough event during the safety follow-up period, a PK, PD, and ADA sample should be collected at the time of the event.

6.2 STUDY TREATMENT

6.2.1 Drug supplies and accountability

Patients will receive doses of either 6.5 grams or 7.5 grams of BIVV009, depending on their body weight. BIVV009 is supplied to the pharmacy for preparation for infusion in either 10 mL vials (18 mg/mL) or 25 mL vials (50 mg/mL). The Sponsor (or designee) will provide the Investigators (or designees) with adequate quantities of the study drug.

BIVV009 drug product will be provided as a sterile, nonpyrogenic, isotonic aqueous solution containing 18 mg/mL or 50 mg/mL BIVV009 with 10 mM sodium phosphate buffer, 140 mM NaCl, 0.02% polysorbate 80 (Tween-80), and water for injection; the pH is 6.1. Each Type 1 glass vial, which has a bromobutyl rubber stopper and an aluminum seal, contains sufficient overfill to account for vial, needle, and syringe loss. Drug product can be used for IV administration only.

BIVV009 should be stored at 2°C to 8°C, protected from light, and kept under secure conditions until immediately before use. It is to be administered via IV infusion according to the instructions given in the Pharmacy Manual for this study. Preparation and accountability procedures for the investigational product including those associated with home infusions (for the US, the Netherlands, Norway, France, Italy, Austria, Germany, and Spain specific amendments) ([Section 10.10](#), Appendix J), whenever applicable, are described in further detail in the Pharmacy Manual.

